#### **4.2.7      ECG Evaluations**

At screening (Visit 1), 12-lead ECG recordings will be obtained in triplicate (within an approximate 2- to 5-minute window) with the participant in a supine position, suitably rested (for at least 5 minutes). At baseline (Visit 2), 12-lead ECGs will be performed in triplicate before administration of the first dose of the IMP; the results should be reviewed by the cardiologist at the site delegated to review all study ECGs (ie. the rater) to confirm that the participant may be dosed (see Exclusion Criterion Number 8).

Subsequently, triplicate 12-lead ECGs (within an approximate 2- to 5-minute window) will be obtained at each dosing visit and the follow-up visit.

All 12-lead ECGs, including those performed at screening, will be of at least 10-second duration.

The confirmation of the decision regarding the participant's eligibility for the study and all ECGs are to be based on local readings. For evaluation of participants with left bundle branch block, a cardiology consultation is strongly recommended.

At a minimum, interval data (QTcF), ventricular rate, and overall interpretation will be reported for each ECG.

The investigator will record on the eCRF whether the results are normal or abnormal (not clinically significant or clinically significant). If recorded as abnormal and clinically significant, the machine-read results and any clinical interpretations must be incorporated into the eCRF, and, if observed after administration of teverelix TFA, the abnormality must also be documented as an AE as described in Section 6.9.2.

**Error! Reference source not found.** presents the quantitative and qualitative ECG parameters that were collected.

**Table 15 ECG Parameters**

ECG Parameters (Unit)
Conduction Times
Ventricular Rate (msec)
QT Interval (msec)
QTcF Interval (msec)

Note: QTcF = QT/CubeRootRR(seconds)

Thresholds for a significant QTcF prolongation are defined as follows:

- QTcF >450 ms
- QTcF >480 ms
- QTcF >500 ms
- An increase from baseline of >30 ms
- An increase from baseline of >60 ms
- QTcF >500 ms or an increase from baseline of >60 ms.

For the qualitative ECG parameters (morphology), it will be recorded whether the parameter at the specific visit was 'Normal' or 'Abnormal'. Each collected quantitative (conduction times) ECG parameter will be classified as 'Normal' or 'Abnormal' at each visit. For all abnormal values, clinical significance (as determined by the Investigator) and any ECG findings should be indicated.

---

Document:

C:\ProgramData\activePDF\Temp\DocConverter\API\Input\\$651f4dc0b253\$FE3041C5883446E892B20AB6D3F0E1BD.docx

Author: [name]

Version and Date: Version 1.0, 21 Apr 2023

Page 41 of 66

---

Based on the criteria presented in Attachment 2, markedly abnormal ECG parameters will be identified at each visit.

---

Document:

C:\ProgramData\activePDF\Temp\DocConverter\API\Input\\$651f4dc0b253\$FE3041C5883446E892B20AB6D3F0E1BD.docx

Author: [name]

Version and Date: Version 1.0, 21 Apr 2023

Page 42 of 66

#### **4.2.8 Vital Signs Evaluations**

Vital signs parameters will be measured at screening, Baseline (Day 0), and Day 28 for both Groups 1 and 2. During Stage 2 these assessments will be performed on the day of the maintenance dose. In both groups this will occur at Days 42, 84, 126, and 168. Additionally vital signs parameters will be measured at follow-up any unscheduled visits for both Groups 1 and 2 (subjects not entered in Stage 3). For subjects entered in Stage 3, vital signs parameters are additionally measured at the final assessment, occurring 1 week after last Stage 3 visit or  $\geq 28$  days after last injection for EW(Early Withdrawal). This is in accordance with the schedule of events (Section 0). These vital signs will be measured with the participant in sitting position for at least 5 minutes.

In the clinic, measurements of the vital signs described below will be made by a trained and authorised person:

- Systolic blood pressure (BP) (mmHg)
- Diastolic BP (mmHg)
- Heart rate (bpm)
- Respiratory rate (breaths per minute)
- Body temperature (°C)

The investigator will evaluate any worsening in vital signs for its clinical relevance as to whether it meets the definition of an AE (see Section 6.9.2). All changes in vital signs that meet the definition of an AE must be documented as an AE in the eCRF.

A manual or automated sphygmomanometer will be used to measure systolic and diastolic BP. Blood pressure results will be recorded in mmHg. Pulse rate will be measured in the radial artery for 60 seconds and will be recorded as beats per minute. If possible, blood pressure and pulse rate should preferably be measured in the same arm at each visit.

Based on the criteria presented in Attachment 2, markedly abnormal vital signs measurements will be identified at each visit.

#### **4.2.9 Predictive Effect of Cardiac Biomarkers**

To assess the predictive effect of cardiac biomarkers for new cardiovascular (CV) events, the following parameters will be collected at Stage 1 (Day 0) and Stage 2 (Day 28, Day 42, Day 84, Day 126, Day 168):

- N-terminal pro-B-type natriuretic peptide (NTproBNP)
- D-dimer
- C-reactive protein (CRP)
- high-sensitivity troponin (hsTn)

### **4.3 Other Measures**

#### **4.3.1 Physical Examination**

A physical examination will be performed at the timepoints specified in **Error! Reference source not found..**

Any abnormalities must be specified in the eCRF and, if observed after administration of teverelix TFA, the abnormality must also be documented as an AE (see Section 5.3.2.3). The complete physical examination will consist of evaluation of general appearance, the skin, head, eyes (including size and reactivity of the pupils), ears, nose, throat, neck, thyroid, lungs, heart, lymph nodes, abdomen, and extremities (to include deep tendon reflexes, clonus, and muscle rigidity).

Any abnormalities noted should be described.

---

Document:

C:\ProgramData\activePDF\Temp\DocConverter\API\Input\\$651f4dc0b253\$FE3041C5883446E892B20AB6D3F0E1BD.docx

Author: [name]

Version and Date: Version 1.0, 21 Apr 2023

Page 43 of 66

#### **4.3.2 Subject Disposition**

Subject disposition data will be included on the 'Informed Consent at Screening visit (visit 1)', 'Subject Eligibility at Screening visit (visit 1)', 'Subject Eligibility at Day 0', 'End of Treatment – Core Study at End of Treatment – Core Study' and 'End of Study – Core Study at End of Study – Core Study' CRF pages when a subject completed or discontinued from the study, along with date and time of informed consent. The following data will be summarized:

- Number of subjects screened and screen failed (with the reasons);
- Number of subjects assigned treatment group;
- Number of subjects completed the study;
- Number of subjects prematurely discontinued\withdrawn (with the reasons);
- The analysis sets defined in Section 3 will be summarised.

#### **4.3.3 Protocol Violations**

Protocol violations are defined as violations that might affect the efficacy or treatment of a subject, and lead to the exclusion of subjects from the analysis sets defined in Section 3.

The following protocol deviations lead to the exclusion from the defined analysis sets:

- Subject did not provide informed consent.
- Subject was not allocated to one of the treatment groups.
- Subject did not take at least one dose of the study medication.
- Prohibited Concomitant Medication received.
- Study visit was outside the permitted window.

The eligibility of all subjects for entry into the study was assessed at Visit 1 Day -6 to -1. A subject should have met all of the inclusion, and none of the exclusion criteria before entry into the study.

The inclusion criteria comprise the following:

1. Is male, aged  $\leq 85$  years ( $\geq 18$  years) at the beginning of the treatment period (Day 0)
2. Has histologically proven advanced adenocarcinoma of the prostate (metastatic or non-metastatic, hormone-sensitive, non-curative), suitable for androgen deprivation therapy
3. Is treatment naïve for any of the following:
  - a. GnRH analogues,
  - b. Androgen receptor antagonists, or
  - c. Androgen synthesis inhibitors (e.g., abiraterone)
4. Agrees to practice contraception during the entire study treatment period and for 3 months after the last dose of IMP is administered:
  - a. Either by using double barrier contraception,
  - b. or, is truly sexually abstinent, when this is in line with the preferred and usual lifestyle of the participant

**Note:** *Periodic abstinence [e.g., calendar, ovulation, symptothermal, postovulation methods for the female partner with childbearing potential] and withdrawal are not acceptable methods of contraception.*

5. Has provided written (personally signed and dated) informed consent before completing any study-related procedure, which means any assessment or evaluation that would not have formed a part of his normal medical care.

The exclusion criteria comprise the following:

---

Document:

C:\ProgramData\activePDF\Temp\DocConverter\API\Input\\$651f4dc0b253\$FE3041C5883446E892B20AB6D3F0E1BD.docx

Author: [name]

Version and Date: Version 1.0, 21 Apr 2023

Page 44 of 66

1. Has abnormal screening and/or baseline laboratory values that suggest a clinically significant underlying disease, or the following laboratory values:
  - a. Liver function test (aspartate aminotransferase [ASAT/SGOT], alanine aminotransferase [ALAT/SGPT]), or total bilirubin exceedingly twice the upper limit of the normal (ULN) range
  - b. Creatinine twice the ULN range
  - c. Uncontrolled diabetes (HbA1c >7.5%) or previously undiagnosed diabetes mellitus with HbA1c >6.5%
2. Has any contraindication to the use of teverelix TFA
3. Has a life expectancy of less than 1 year
4. Has T levels <2.0 ng/mL at screening
5. Has a medical history of bilateral orchidectomy
6. Using any of the following prohibited treatments:
  - a. Within 25 weeks prior to screening: dutasteride
  - b. Within 12 weeks prior to screening: finasteride
  - c. Current use of any of the following:
    - i. Anti-androgen therapy, including T replacement therapy and 5  $\alpha$ -reductase inhibitor treatment etc. (Spironolactone is a permitted concomitant treatment).
    - ii. GnRH analogues, androgen receptor antagonists
    - iii. Androgen synthesis inhibitors (e.g., abiraterone)
    - iv. Any other medication or herbal product that may affect hormone levels and might, therefore, confound interpretation of the study results (e.g., St. John's wort)
7. Has neurological disease, psychiatric disease, drug, or alcohol abuse, which could interfere with the participant's proper compliance
8. Has a history of myocardial infarction, unstable symptomatic ischaemic heart disease, any ongoing cardiac arrhythmias of grade >2 (chronic stable atrial fibrillation on stable anticoagulant therapy is allowed), thromboembolic events (e.g., deep vein thrombosis, pulmonary embolism, or symptomatic cerebrovascular events), or any other significant cardiac condition (e.g., pericardial effusion, restrictive cardiomyopathy) within the 6 months prior to screening
9. Has congenital long QT syndrome or ECG abnormalities at screening of:
  - a. Q-wave infarction, unless identified  $\geq$  6 months before screening
  - b. Fridericia corrected QT interval (QTcF interval) >480 msec. If QTcF is prolonged in a participant with a pacemaker, the participant may be enrolled in the study upon discussion with the project clinician.If the QTcF interval is 450-480 msec, inclusive, in a participant with current use of medications with known effects on QT interval, the participant may be enrolled in the study following discussion with the Medical Lead

**Note:** Cardiac arrhythmia grading:

- o Bradyarrhythmias (HR <60/min)
- o Tachyarrhythmias (HR >100/min)
- o Supraventricular arrhythmias – arrhythmias that originate in the sinoatrial node, atrial myocardium or atrioventricular node (regular QRS complex)
- o Ventricular arrhythmias – arrhythmias that originate below the atrioventricular node (wide QRS complex)

10. Has known or suspected severe renal impairment
11. Has a medical history of diagnosis of, or treatment for, another malignancy within the 2 years prior to administration of the first dose of IMP, or previous diagnosis of another

---

Document:

C:\ProgramData\activePDF\Temp\DocConverter\API\Input\\$651f4dc0b253\$FE3041C5883446E892B20AB6D3F0E1BD.docx

Author: [name]

Version and Date: Version 1.0, 21 Apr 2023

Page 45 of 66

malignancy with evidence of residual disease. Participants with nonmelanoma skin cancer or carcinoma in situ of any type are not excluded if they have undergone complete resection

12. Is currently using Class IA (e.g., quinidine, procainamide) or Class III (e.g. amiodarone, sotalol) antiarrhythmic medications
13. Has uncontrolled hypertension despite appropriate medical therapy (sitting blood pressure [BP] of >180 millimetres of mercury [mmHg] systolic and >95 mmHg diastolic at 2 separate measurements taken no more than 60 minutes apart during the screening visit). Participants with isolated systolic BP measurements >180 mmHg may be rescreened. Participants with isolated systolic BP measurements 141 to 180 mmHg or isolated diastolic BP measurements ≥95 mmHg, although eligible, should be referred for further management of hypertension if indicated
14. Has known, previously diagnosed human immunodeficiency virus (HIV) infection, active chronic hepatitis B or C, life-threatening illness unrelated to prostate cancer, or any serious medical condition that could, in the investigator's opinion, potentially interfere with participation in this study. Specific screening for chronic viral illness is at the discretion of the site and/or local Institutional Review Board (IRB)
15. Has been exposed to another investigational drug within the 3 months prior to screening
16. Has anticipated non-availability for study visits/procedures
17. Plans to undergo surgery during the study period
18. Known presence of liver metastases

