8.1.11 Software used for Statistical Analysis

The SAS® software version 9.2 (SAS® Institute) or higher will be used for the statistical analysis and for the reporting of this study. PK/PD analyses will be performed with Phoenix® WinNonlin® Version 6.3 or higher (Certara L.P).

8.1.12 **Determination of Sample Size**

Initially, since no confirmatory analyses were planned, no sample size calculations were performed. A total of 24 participants was deemed sufficient for 1 treatment group to obtain at least 20 evaluable participants (Day 168 visit completed).

Subsequently the Sponsor undertook a formal sample size calculation so that the Group 2 data could be used to support the dose selection for future Phase 3 clinical trials.

A sample size of 60 has been chosen on clinical grounds. This number gives good power to detect a minimum proportion of 90% subjects achieving castration with central lab serum T <0.5 ng/mL or 1.73 nmol/L at Day 28 from the per protocol population. It is based on the null hypothesis that the true response rate is 74.5%, the average response rate in previous Teverelix trials not achieving 90% response rate. This is tested using a two-sided test with a 5% alpha level against the alternative hypothesis that the response rate is 90%, the minimally clinically relevant response rate. Based on this, fifty participants give power of 80%. Assuming a dropout rate of 16%, sixty patients are recommended.

Sixty patients will ensure acceptable precision for justification for further analysis of this regimen in Phase 3. A true 90% response rate in this instance would give a confidence interval of (79,96) and if 10 subjects drop out, and interval of (78,97). A true 95% response rate with 60 participants would give a confidence interval of (86,99) and if 10 subjects drop out, an interval of (85,99).

8.2 **Data Management**

Data management will be performed using Oracle Clinical Version 3.3 or later running on 2 Microsoft Windows NT servers. Details will be defined in the data management manual, which will be signed by the Sponsor and the Clinical Research Organisation (CRO) prior to start of the data entry.

9 Data Handling and Data Quality Assurance

9.1 **Data Management**

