#### **3.4 Intention-to-Treat (ITT) Analysis Set**

All participants included in the safety population and for whom the primary endpoint is evaluable will be included in the ITT analysis set. Participants for whom the primary efficacy measure is evaluable are those who have a non-missing central lab serum T record at Day 28.

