### **3.7 Per Protocol (PP) Analysis Set**

All participants included in the ITT analysis set who complete the study without major protocol violation will be included in the PP analysis set. Participants with major protocol violations will be excluded.

Protocol Violations will be classified as either 'major' or 'minor' in collaboration with the Sponsor. The criteria for this assessment will be defined before database lock. Patient inclusion or exclusion from this population will be confirmed following data review and prior to database lock. Listings will be prepared to show the eligibility of all participants prior to database lock. These listings will be presented in a Data Review Meeting.

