#### **4.1.1 Primary Efficacy Measure**

The primary efficacy measure is the proportion of subjects achieving castration with central lab serum T <0.5 ng/mL or 1.73 nmol/L at Day 28. The denominator is the number of subjects who have a non-missing central lab T record at Day 28 in the relevant population.

---

Document:

C:\ProgramData\activePDF\Temp\DocConverter\API\Input\\$651f4dc0b253\$FE3041C5883446E892B20AB6D3F0E1BD.docx

Author: [name]

Version and Date: Version 1.0, 21 Apr 2023

Page 29 of 66

The primary parameter analysis will be performed on the PP analysis set. In addition, a sensitivity analysis will be performed on the ITT analysis set.

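### SAP 4.3.3 makes any out-of-window visit a ground for exclusion from the analysis sets, contradicting SAP 3.3, 3.4 and 3.7 and leaving the primary Day 28 set without a single definition

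*SAP*

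**What the plan says.** SAP 4.3.3 describes protocol violations as those that might affect efficacy or treatment and that "lead to the exclusion of subjects from the analysis sets defined in Section 3". It then introduces a list: "The following protocol deviations lead to the exclusion from the defined analysis sets". The last item is "Study visit was outside the permitted window". The item does not say which visit, how far outside the window, or which analysis set.

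SAP 3.7 builds the PP set differently: "All participants included in the ITT analysis set who complete the study without major protocol violation will be included in the PP analysis set". On grading it adds: "Protocol Violations will be classified as either 'major' or 'minor' in collaboration with the Sponsor", with criteria to be fixed before database lock and membership confirmed at data review. Protocol 8.1.1 takes the same approach.

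SAP 3.3 puts every man who received any dose into the Safety set. SAP 3.4 defines the ITT set by the presence of a Day 28 result: "Participants for whom the primary efficacy measure is evaluable are those who have a non-missing central lab serum T record at Day 28". Neither has a window condition.

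The PP set carries the primary result: "The primary parameter analysis will be performed on the PP analysis set" (SAP 4.1.1). The ITT set is the sensitivity analysis. Protocol Section 4 states that enrolled men who cannot be analysed in the PP set are not replaced.

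**The concern.** Two parts of one SAP give different rules for the set that carries the primary result, and nothing says which prevails. SAP 4.3.3 is specific and unconditional. SAP 3.7 is general, with its criteria still to be written. Two programmers could build different PP sets from the same text.

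The literal rule also produces the worse analysis. A man seen one day late on Day 2, or outside the three-day allowance on Day 119, would be dropped although neither visit bears on his Day 28 central testosterone. Because 4.3.3 refers to all the Section 3 sets, he would leave ITT as well, which is the set meant to check the PP result.

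SAP 6.8 says that a response rate above 90% in PP but below it in ITT will be considered in interpretation. With 50 men each man is worth 2 percentage points, so membership decides how that comparison reads. In an open-label trial it should not be left to be settled at data review.

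**Working it through.** **Inputs from the documents.** Protocol 8.1.12: null rate 74.5% ("It is based on the null hypothesis that the true response rate is 74.5", in per cent), alternative 90%, two-sided 5% test, 50 evaluable for 80% power, 16% dropout, 60 enrolled. SAP Tables 4 and 19: 18 post-dose visits to Day 168. Five have a zero-day window (Days 1, 2, 3, 4, 7), four allow 1 day (Days 10, 12, 14, 21) and nine allow 3 days (Days 28, 35, 42, 77, 84, 119, 126, 161, 168).

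**Assumption.** The documents give no out-of-window rate. Let q be the probability that a visit is out of window, the same for every visit and independent between visits. A range of q is shown.

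**Step 1: the plan's own figure.** Normal approximation: power = Φ[(p1 − p0 − 1.96·√(p0(1−p0)/n)) / √(p1(1−p1)/n)]. At n = 50 this is Φ[(0.155 − 1.96 × 0.0616)/0.0424] = Φ(0.81) = 79%, close to the stated 80%. The exact binomial test needs at least 44 of 50 responders (upper tail 0.016 under the null) and has power 77%. For dropout, 50/(1 − 0.16) = 59.5, rounded up to 60, as stated.

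**Step 2: men with at least one out-of-window visit under the literal rule.** The share is 1 − (1 − q)^18.

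**Step 3: expected PP set.** Without other losses it is 60 × (1 − q)^18. With the planned dropout as well it is 60 × 0.84 × (1 − q)^18 = 50.4 × (1 − q)^18.

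| q | share with ≥1 late visit | expected PP, no other loss | expected PP, 16% dropout as well |
|---|---|---|---|
| 0.5% | 9% | 54.8 | 46.1 |
| 1% | 17% | 50.1 | 42.1 |
| 2% | 31% | 41.7 | 35.0 |
| 5% | 60% | 23.8 | 20.0 |

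**Step 4: break-even.** If the 10 spare men cover every loss, an expected 50 remain when (1 − q)^18 ≥ 50/60, that is q ≤ 1 − (50/60)^(1/18) = 1.0%.

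**Step 5: probability of reaching 50 (binomial, 60 men).** With no other loss: 98.7% at q = 0.5%, 59.3% at 1%, 1.1% at 2%. With 16% dropout as well: 63.8% with no window exclusions at all, then 14.5% at 0.5% and 1.4% at 1%.

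**Step 6: power at a smaller set.** At n = 35 the exact test needs 32 responders and has power 53%; the normal approximation gives Φ[(0.155 − 1.96 × 0.0737)/0.0507] = Φ(0.21) = 58%.

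**Step 7: if only the Day 28 window counts.** 50.4 × (1 − q) gives 49.9, 49.4 and 47.9 men at q = 1%, 2% and 5%.

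**The case against.** The strongest reply is that SAP 3.7 and Protocol 8.1.1 already govern. Only major violations exclude, criteria are fixed in advance, and a trivially late Day 119 visit need not be graded major. SAP 4.3.3 itself speaks of violations that might affect efficacy or treatment. Its bullets can be read as a mixed list, each serving a different set: no dose concerns Safety, and prohibited medication overlaps with the separate set in SAP 3.5, which would have little purpose if every bullet already applied to ITT. This is a fair reading. It means that the literal rule cannot be called the SAP's settled intention, for PP, ITT or Safety. It does not remove the conflict, because 4.3.3 says that the listed items lead to exclusion and never refers to the grading.

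A reader might infer that 50 evaluable men are unlikely. The documents do not support that. SAP 6.8 expects few violations, no rate is given, and the 10 spare men can be read as covering all PP losses, since Protocol 3.1 and Section 4 plan 60 enrolled to obtain 50. Independence between visits also overstates the loss. With q = 2% and an assumed within-man correlation of 0.1 to 0.2 (beta-binomial), 19% to 14% of men have any late visit instead of 31%, leaving about 41 to 44 men after dropout, not 35. Exact power moves in steps as well (69% at n = 37, 74% at n = 43), so the 53% at n = 35 should be read beside the normal-approximation figure.

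A reader might also infer that the window rule selects men who stay castrate. That selection comes mainly from the requirement in SAP 3.7 to complete the study. Men withdrawn early have fewer visits at which to breach a window, so the window rule alone could run the other way.

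**Conclusion.** The point holds as an internal contradiction with a real cost. SAP 4.3.3 states an unlimited window exclusion that conflicts with SAP 3.7 and Protocol 8.1.1 on PP, and with SAP 3.3 and 3.4 on Safety and ITT. If followed, it discards valid Day 28 results from the primary analysis.

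The size depends on a rate that the documents do not give. With independent visits and the full 16% dropout, the PP set would be about 42, 35 or 20 men at 1%, 2% or 5% per visit. With no other losses, an expected 50 survive up to about 1%. Clustering of late visits within men would make the loss smaller. A shortfall below 50 is therefore possible under the literal rule but is not established.

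This should be fixed before database lock. It falls short of a must-fix because SAP 3.7 offers a workable competing rule and the size rests on assumptions.

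**What to change.** In SAP 4.3.3, delete the window bullet as a stand-alone exclusion and state that:

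- (a) the major/minor grading in SAP 3.7 governs PP membership;
- (b) for the Day 28 endpoints, a window deviation is major only if the Day 28 central testosterone sample falls outside Day 25 to Day 31, the Table 19 window;
- (c) other out-of-window visits are handled at visit level under Table 19;
- (d) window deviations at other visits never remove a man from the Safety or ITT set.

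Item (b) adds no new restriction: Table 19 already assigns a sample to Day 28 only within 3 days of the planned day. Items (a) and (d) are needed because restricting the bullet to Day 28 would, on its own, leave the relation between 4.3.3 and 3.7 unstated.

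The cost is SAP wording only. The downside is that a few men with minor timing deviations stay in the PP set.
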